APPENDIX 2: ERT WITHDRAWAL SCHEDULE OF EVENTS

PROCEDURE*	ERT Withdrawal Visit (a)	ERT	Withd	irawal +/-	ERT Withdrawal Follow- Up Visit (within 12 weeks of ERT withdrawal) (c)					
		1	2	3	4	6	8	10	12	
Concomitant Medications	X	Х	Х	Х	Х	Х	Х	Х	Х	X
Physical Examination	Х									Х
Vital Signs (d)	Х									Х
AE Assessment	X	Х	Х	Х	Х	Х	Х	Х	Х	X
ERT Administration Log	X	Х	Х	Х	Х	Х	Х	Х	Х	Х
Clinical Laboratory Tests	X									X
Liver Panel (e)	X	Х	Х	Х	Х	Х	Х	Х	Х	X
GAG Testing in Urine	X	Х	Х	Х	Х	Х	Х	Х	Х	X
IDS / GAG Testing in Blood	Х	X (g)	Х	X (g)	Х	Х	Х	Х	Х	Х
PFTs (f)	X									Х
6MWT (f)	X									X
ERT Clinical Assessment										Х

* Assessments associated with ERT withdrawal that are duplicated at regular scheduled study visits should be waived if visits are combined (see Appendix 1).

a) ERT Withdrawal visit may occur at or at any time after the Week 12 visit (refer to Section 11.4 for additional guidance).

- b) ERT Withdrawal Monitoring visits will take place on a weekly basis for the first 4 weeks, and on a biweekly basis for the last 8 weeks following the ERT Withdrawal visit until the ERT Withdrawal Follow-Up visit. ERT Withdrawal Monitoring visits have assessments that do not require evaluation at the clinical site, and may therefore be conducted at home if the subject is remote. Blood and urine samples at these visits may be collected by a qualified home health nurse. Assessments for AEs and concomitant medications may be conducted by study staff over the phone.
- c) The ERT Withdrawal Follow-Up visit can occur at any time up to 12 weeks after ERT withdrawal at the discretion of the Principal Investigator. ERT does not need to be restarted at the end of the ERT Withdrawal Follow-Up visit.
- d) Vital signs (weight, systolic/diastolic blood pressure, heart rate, respiratory rate, and temperature; refer to the Study Reference Manual).
- e) Liver panel does not need to be drawn as a separate sample if Clinical Laboratory Tests are obtained at the same visit.
- f) As permitted by subject's capacity.
- g) May be waived for pediatric subjects (cohorts 5 through 8) at the discretion of the Principal Investigator to minimize required blood volumes.

Weight of	Oral Prednisone (mg/day)														
Subject (kg)	Day -2 to Day 0	Week 1	Week 2	Week 3-16	Week 17-19	Week 20									
> 60	60	60	30	15	5	STOP									
55	60	60	30	15	5	STOP									
50	50	50	25	15	5	STOP									
45	45	45	25	15	5	STOP									
40	40	40	20	10	5	STOP									
35	35	35	20	10	5	STOP									
30	30	30	15	10	5	STOP									
<30	1 mg/kg	1 mg/kg	0.5 mg/kg	0.25 mg/kg	0.25 mg/kg every other day	STOP									

APPENDIX 3: IMMUNOSUPPRESSION REGIMEN

Prednisone or equivalent corticosteroid regimen is commenced 2 days prior to Day 0 of SB-913 infusion and given once daily unless otherwise stated. Subject's liver function will be monitored twice a week while on prednisone or equivalent corticosteroid. Blood for liver panel shall be drawn 2-4 days apart when possible, except for the first week when it will be drawn on the Day 1 and Day 7 visits. Tapering of prednisone or equivalent corticosteroid will only proceed if ALT/AST activity levels are stable or declining (based on the 2 assessments of the preceding week).

If subjects develop increased ALT > 2 fold Baseline while on prednisone or equivalent corticosteroid or after stopping prednisone or equivalent corticosteroid, the prednisone or equivalent corticosteroid regimen may be adjusted or restarted at the Principal Investigator's discretion after consultation with the Medical Monitor. Twice a week liver panel testing should continue until the prednisone or equivalent corticosteroid course has been terminated.

An ACTH stimulation (cosyntropin) test will be performed prior to the first prednisone or equivalent corticosteroid dose and again during Week 20 or at the end of the scheduled taper to ensure that the adrenal cortical function has not been suppressed. Should prednisone or equivalent corticosteroid treatment be repeated due to increased transaminase activity, the ACTH stimulation test will be repeated at the end of taper at the Principal Investigator's discretion.

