The 3 components of SB-913 (ZFN1, ZFN2, and hIDS Donor) will each be added to 200 mL of diluent (refer to the Pharmacy Manual) and adjusted to 0.25% human serum albumin. Total infusion volumes will depend on a subject's cohort assignment and body weight (kg). IV infusions will be administered while the subject is in the hospital or acute care facility (refer to the Pharmacy Manual).

The subject will remain in the hospital or acute care facility for at least 24 hours after completion of SB-913 infusion for observation, and will be discharged when all AEs and vital signs (temperature, heart rate, respiratory rate, and blood pressure) are stable.

After being discharged from the hospital or acute care facility, study visits are scheduled on Day 7; Weeks 2, 4, 6, 8, 12, 16, 20, 24, 28, 32, 36, 40, 44, 48, and 52; and Months 15, 18, 21, 24, 27, 30, 33, and 36 (see Section 6 and Appendix 1).

Liver function tests (aspartate aminotransferase [AST], alanine aminotransferase [ALT], total and direct bilirubin, alkaline phosphatase, LDH, albumin, and total protein levels) will be conducted for evaluation of AAV mediated immunogenicity twice a week during the first 20 weeks after SB-913 infusion and may be conducted at home if the subject is remote. Blood samples for liver function tests will be drawn 2-4 days apart when possible, except for the first week when they will be drawn on the Day 1 and Day 7 visits. Liver function tests will subsequently be conducted at all study visits.

Previous studies with IV AAV8 FIX gene therapy have shown that liver transaminitis due to AAV immunogenicity occurs between 2 and 9 weeks after infusion and resulted in loss of FIX expression, and that rapid institution of prednisone can control this immunogenicity. If in spite of pretreatment with prednisone or equivalent corticosteroid in this study there is evidence of transaminitis, the dose of prednisone or equivalent corticosteroid will be increased on a case-by-case basis, and liver function will be assessed twice a week until normalization of liver enzymes, and then per protocol thereafter.

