c. Serum pregnancy test will be performed at Screening and Baseline visits. Urine pregnancy test will be performed on the Day 0 visit if >7 days from Baseline pregnancy test. Urine pregnancy tests will be performed until Week 48 or until 3 consecutive plasma samples are negative for AAV2/6, whichever occurs first.

d. Liver panel does not need to be drawn as a separate sample if samples for Clinical Laboratory Tests are obtained at the same visit.

SB-913-1602

Clinical Study Protocol

- e. Liver panel will be performed twice a week for the first 20 weeks post-SB-913 infusion, and may be conducted at home if the subject is remote. Blood samples will be drawn 2-4 days apart when possible, except for the first week when it will be drawn on the Day 1 and Day 7 visits. Liver function tests will subsequently be conducted at all indicated study visits.
- f. For adult subjects (cohorts 1 through 4), the assay will be performed on blood or saliva samples; for pediatric subjects (cohorts 5 through 8), saliva samples are preferred.
- g. During Screening, samples for GAG testing in urine will be collected on 3 separate days, each collection occurring at least 7 days after the previous. All samples for GAG testing in the urine must be collected at least 7 days after ERT administration [+/-1 day] but prior to the next ERT infusion.
- h. For IDS/GAG testing in blood, samples must be obtained 7 days after ERT administration (+/- 1 day) and prior to the next ERT infusion. GAG and IDS levels in blood will both be measured concurrently from the same blood sample.
- i. Each type of sample (plasma, saliva, urine, stool, semen) will be collected until 3 consecutive specimens of that sample type are reported as negative or undetectable for vector genome. Collection of semen samples may be waived for male pediatric subjects (cohorts 5 through 8) at the discretion of Principal Investigator.
- j. As permitted by subject's capacity. Neurocognitive abilities testing in pediatric subjects will be done by VABS-II and by WASI-II, WPPSI-IV, or BSID-III, as appropriate based on the Neurocognitive Abilities Assessment performed at Screening.
- k. Baseline MRI of brain and cervical spine may be obtained at the Screening visit (together with MRI for liver) instead of at the Baseline visit at Principal Investigator's discretion.

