#### 10.3 Appendix C: Immunosuppression Regimen

Weight of Subject			Oral Predniso	ne (mg/day)		
(kg)	Day -2 to Day 1	Week 1	Week 2	Week 3-16	Week 17-19	Week 20
≥ 60	60	60	30	15	5	STOP
55	60	60	30	15	5	STOP
50	50	50	25	15	5	STOP
45	45	45	25	15	5	STOP
40	40	40	20	10	5	STOP
35	35	35	20	10	5	STOP
30	30	30	15	10	5	STOP
<30	1 mg/kg	1 mg/kg	0.5 mg/kg	0.25 mg/kg	0.25 mg/kg every other day	STOP

Prednisone or equivalent corticosteroid regimen is commenced 2 days prior to Day 0 of SB-913 infusion and given once daily unless otherwise stated. Subject's liver function will be monitored twice a week while on prednisone or equivalent corticosteroid. Liver panel shall be drawn 2-4 days apart when possible, except for the first week when it will be drawn on Day 1 and Day 7 visits. Tapering of prednisone or equivalent corticosteroid will only proceed if ALT/AST activity levels are stable or declining (based on the 2 assessments of the preceding week).

If subjects develop increased ALT > 2 fold baseline while on prednisone or equivalent corticosteroid or after stopping prednisone, the prednisone regimen or equivalent corticosteroid may be adjusted or restarted at the Principal Investigator's discretion after consultation with the Medical Monitor. Twice a week liver panel testing should continue until the prednisone course or equivalent corticosteroid has been terminated.

An ACTH stimulation (cosyntropin) test will be performed prior to the first prednisone or equivalent corticosteroid dose and again at the end of the scheduled taper to ensure that the adrenal cortical function has not been suppressed. Should prednisone or equivalent corticosteroid treatment be repeated due to increased transaminase activity, the ACTH stimulation test will be repeated at the end of taper at the Principal Investigator's discretion.

CONFIDENTIAL Page 28 of 28

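### After transaminitis, the synopsis and Section 3.5 keep liver panels twice weekly until enzymes normalize, but Appendix 3, Section 9.13 and the visit schedules omit that condition, so a subject with raised enzymes could drop to 4-weekly panels.

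*Protocol*

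**What the plan says.** **The rule specific to transaminitis.** The synopsis (Treatment Plan & Schedule) and Protocol Section 3.5 say that if transaminitis appears despite prophylactic steroids, the steroid dose is raised case by case and "liver function will be assessed twice a week until normalization of liver enzymes, and then per protocol thereafter". The ordinary schedule resumes only after normalization.

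**The steroid appendix.** Protocol Appendix 3 has a paragraph that opens "If subjects develop increased ALT > 2 fold Baseline while on prednisone or equivalent corticosteroid" and also covers a rise after steroids have stopped. Its response is that "the prednisone or equivalent corticosteroid regimen may be adjusted or restarted at the Principal Investigator's discretion after consultation with the Medical Monitor". It ends the monitoring instruction with "Twice a week liver panel testing should continue until the prednisone or equivalent corticosteroid course has been terminated". SAP Appendix C reads "Twice a week liver panel testing should continue until the prednisone course or equivalent corticosteroid has been terminated". On tapering, Appendix 3 says "Tapering of prednisone or equivalent corticosteroid will only proceed if ALT/AST activity levels are stable or declining".

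**The operational schedules.** Appendix 1 footnote e says "Liver panel will be performed twice a week for the first 20 weeks post-SB-913 infusion" and then "Liver function tests will subsequently be conducted at all indicated study visits". SAP Appendix A carries the same footnote. Section 6.8 gives twice-weekly panels to Week 20 and then one every 4 weeks to Week 52. Section 6.9 gives 3-monthly visits in Years 2 and 3. Section 9.13 sets 20 weeks as a minimum and moves panels to study visits once steroids are discontinued.

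**A neighbouring difference.** Appendix 1 footnote l makes the repeat ACTH stimulation test mandatory after a continued or repeated steroid course. Appendix 3 leaves it to the investigator after a repeated course. The SAP copies differ in the same way.

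**The concern.** Transaminitis is the first key anticipated risk in Section 12.2, and that section sends sites to Section 9.13 for liver monitoring. Section 9.13 is one of the places without the normalization condition. A site that follows it, or Appendix 3, as written could cut panels back just as steroid cover ends in a subject whose enzymes have not settled. Section 3.5 reports that transaminitis in earlier AAV8 work led to loss of expression and that prompt prednisone can control it. Prompt treatment depends on a panel being drawn.

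The safety committee triggers in Sections 11.2 and 12.3 do not replace that panel. A rise seen only in the laboratory reaches them only after a sample is taken, and under Section 10.3 a Grade 1 or 2 laboratory abnormality is an AE only if the investigator judges it clinically significant.

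**Working it through.** The plan gives no figure to reproduce. The check sets the rules side by side and then counts scheduled panels.

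| Place | Twice weekly until | Then | Normalization condition |
|---|---|---|---|
| Synopsis; Protocol 3.5 | enzymes normalize | ordinary schedule | yes |
| Protocol Appendix 3; SAP Appendix C | steroid course ends | not stated | no |
| Protocol 9.13 | at least Week 20 | study visits once steroids stop | no |
| Protocol 6.8 | Week 20 | every 4 weeks to Week 52 | no |
| Protocol Appendix 1 and SAP Appendix A, footnote e | Week 20 | indicated visits | no |

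**Where they part.** Through Week 20, and during any continued or restarted course, every section gives twice-weekly panels. They diverge in two situations:

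1. Enzymes are raised but not rising when steroids stop. The taper condition allows this.
2. Enzymes rise after steroids have stopped and the investigator does not restart them. Appendix 3's endpoint has then already passed.

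**Panels in Weeks 20 to 24.** Section 3.5: 2 × 4 = 8. Operational schedule: 1, at Week 24. Difference: 7. A subject in ERT-withdrawal monitoring Weeks 1 to 4 over the same period would have 4 (Appendix 2).

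**Gap between visits.** Week 20 is Day 140 ± 7 (133 to 147) and Week 24 is Day 168 ± 7 (161 to 175). Nominal gap: 168 − 140 = 28 days. Shortest: 161 − 147 = 14. Longest: 175 − 133 = 42. Twice-weekly samples are meant to fall 2 to 4 days apart.

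**Mean wait for the next panel.** For a change starting at a uniformly random time, the mean wait is ΣL² / (2ΣL), where L is the spacing.
- Alternating 3 and 4 days: (9 + 16) / (2 × 7) = 1.8 days.
- 28 days: 28² / (2 × 28) = 14 days.

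This compares the rules for a subject already known to have transaminitis. It does not apply to first detection after Week 20 in a subject with no earlier rise, who is on scheduled visits under either rule.

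**Longer horizons.** Weeks 20 to 52: 2 × 32 = 64 panels against 8. After Week 52, per 13 weeks: 2 × 13 = 26 against 1. These are ceilings, because they assume that enzymes stay raised throughout.

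All counts assume no unscheduled tests.

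**The case against.** A reader might infer that the protocol contains two irreconcilable rules. It does not. Appendix 3 asks for testing up to the end of the course without forbidding more, Section 9.13 sets a minimum, and testing to the later endpoint satisfies every section. The harm requires a site to overlook a mandatory instruction that appears twice. This objection stands, and it limits the point to an omitted condition and a missing cross-reference.

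A reader might also take the AAV8 experience as evidence of particular danger after Week 20. Section 3.5 places that transaminitis at 2 to 9 weeks after infusion, wholly inside the undisputed twice-weekly period. A rebound when steroids stop is plausible, but the documents do not quantify it.

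Nor do the documents support reading Appendix 3's ALT wording as leaving AST rises uncovered. Section 8.1 refers to aminotransferases generally, and Section 3.5 to transaminitis and liver enzymes.

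Finally, 8 against 1 is near the worst case. It needs the Section 3.5 rule to be missed, steroids to stop at Week 20 and enzymes to stay raised for four weeks. Section 3.5 expects the steroid dose to be increased, and a longer course keeps twice-weekly testing in force.

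What survives is that neither the taper condition nor the discretionary restart requires normal enzymes, and the sections sites are most likely to work from do not say that Section 3.5 does.

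**Conclusion.** The point holds as a bounded inconsistency in a subject-safety instruction, and it is worth correcting. Appendix 3, Section 9.13, Section 6.8 and footnote e omit the stopping condition that the synopsis and Section 3.5 impose. Applied as written, they can put a subject with unresolved enzymes on 4-weekly panels, or 3-monthly panels after Week 52. The loss is up to 7 panels per affected subject in the first four weeks after Week 20, under the assumptions stated above.

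The share of subjects affected cannot be derived from the documents and is probably small. A Grade 3 or higher AE not attributed to MPS II or its treatment would still pause dosing and convene the safety committee. No analysis or sample-size figure changes. The opening of Section 8.1 and the Laboratory Manual were not available for this check, so a bridging sentence there cannot be excluded.

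The ACTH difference is separate and minor.

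**What to change.** In Protocol Appendix 3 and SAP Appendix C, replace the sentence on twice-weekly testing with:

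> In any subject with evidence of transaminitis (ALT or AST), during or after the steroid course and whether or not steroids are restarted, twice-weekly liver panels continue until the later of the end of the steroid course and normalization of liver enzymes (Section 3.5).

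Refer to this rule in Sections 6.8 and 9.13 and in footnote e of Protocol Appendix 1 and SAP Appendix A. Do not add an early exit for mild stable elevations or a numerical trigger narrower than evidence of transaminitis. Either would loosen what Section 3.5 already gives.

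As a separate minor edit, align the repeat ACTH test in Appendix 3 and SAP Appendix C with footnote l, preferably on the mandatory wording, since adrenal insufficiency is a listed steroid risk in Section 8.2.

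**Cost.** A protocol wording amendment, a matching SAP edit and a letter to sites. Compared with the operational schedule, the rule adds about 7 panels per affected subject per 4 weeks, all already required by Section 3.5. The added ACTH tests are already required by footnote l.

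Section 9.31 asks for pediatric draws to be minimized and normally limits them to 0.8 mL/kg in 24 hours. At the 20 kg minimum weight that is 0.8 × 20 = 16 mL. Panel volume is not given; if it is 1 to 5 mL, one panel uses 1/16 to 5/16, about 6% to 31%, of the daily limit, with panels 2 to 4 days apart.

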APPENDIX 4: INSTRUCTION FOR LIVER BIOPSY SAMPLE COLLECTION AND TISSUE PREPARATION

SB-913 uses ZFN-gene specific targeted insertion of a hIDS donor transgene into the liver albumin genome locus in subjects with MPS II to provide long-term production of hIDS. To determine the efficiency of SB-913, liver tissue will be obtained by liver biopsy for analysis by histopathologic examination, testing for GAG levels, and site specific molecular analysis at the albumin locus. AFP levels will be monitored throughout the study, and abnormal results will be investigated by clinical evaluation and MRI. Any subject who has an elevated AFP and/or an MRI mass suspicious for HCC or greater than 2 cm will undergo liver biopsy. Histopathologic examination and integration site analysis will be performed to determine the origin and nature of the tumor.

Liver Biopsy Sample Collection and Tissue Preparation

Liver biopsy will be obtained at selected visits unless contraindicated by a Principal Investigator or physician. The liver biopsy should be divided into 3 samples when possible. One liver biopsy sample will be collected in 10% neutral buffered formalin and processed for histopathological evaluation. Two liver biopsy samples will be flash frozen in liquid nitrogen. Samples may be stored in a -80°C freezer before shipment. The weight of liver tissue obtained from each biopsy sample will be forwarded to Sangamo.

The efficiency of SB-913 in targeting insertion of hIDS donor transgene to the liver will be measured by site specific molecular analysis of integration events at the albumin locus.

Additionally, the frequency of other genomic modification events like small insertions and deletions (indels) will be determined by Next Generation Sequencing (NGS) at the albumin locus and at the SMCHD1 locus, the only known off-target site of SB-913.

In addition, for any subject who undergoes liver biopsy due to an elevated AFP and/or an MRI mass suspicious for HCC, the albumin locus will be sequenced by NGS to examine the genetic diversity at the albumin ZFN cleavage site, which may provide information about the clonal origin of the suspicious mass. A single or limited number of modified albumin genotypes or AAV integration sites would indicate that the cells were derived from the clonal expansion of modified hepatocytes. A similar sequencing analysis will also be performed on the SMCHD1 locus to evaluate the genetic diversity at the only known off-target site of SB-913.

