Given the rate of albumin production by the liver (12-25 g/day), it can be estimated that the conversion by SB-913 of as little as 0.01% of albumin alleles to hIDS synthesis would yield potentially therapeutically beneficial IDS levels (>1% of normal) in plasma (Muenzer et al. 2006; Elaprase FDA summary of approval). The loss of such a small proportion of albumin production is expected to have no adverse consequences. At the individual cell level, the targeted locus is

completely dispensable, since albumin has no autocrine role. At the organism level, heterozygous disruption of albumin yields no symptoms, and even homozygous disruption is tolerated as described above. Therefore, disrupting < 1% of the albumin alleles is predicted to have no adverse phenotype. Moreover, given the intronic location of the ZFN target site, ZFN cleavage and subsequent DNA repair in the absence of hIDS integration (e.g., small insertion and deletion mutations at the site of ZFN cleavage) will be functionally inert with respect to albumin expression. A recent review of the genetic targeting of the albumin locus to treat hemophilia in murine models highlights the usefulness of targeting a highly active heterologous gene like albumin; neither transaminitis nor perturbations in serum albumin levels were observed, and few off-target integration sites were detected (Davidoff & Nathwani 2016).

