# 4.5 Handling of Dropouts or Missing Data

If laboratory result is below detection limit, it will be imputed to half of detection limit in table and figure. The result will be listed as is in listings.

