#### 6. ENDPOINT ANALYSIS

Since this is a single-dose study to evaluate safety, analyses will be descriptive and exploratory in nature. Change from the preceding year values may be calculated for selected clinical and laboratory parameters.

If there is a result with a "<" sign, will drop the sign and use half of the number for analysis. If the result is below detection limit, it will be imputed to half of detection limit in table and figure. The result will be listed as is in listings.

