#### **6.3** Exploratory Endpoints and Analyses

Exploratory endpoints will be summarized by presenting descriptive statistics of actual values and changes from baseline at each visit. A by-subject listing will also be provided. The exploratory endpoints consist of the changes from baseline over time in the following assessments:

 Percentage and durability of gene modification at the albumin locus in liver tissue obtained at biopsy

Assessments will be conducted at Baseline, Week 24, and Week 48

FVC measured by PFTs

Assessments will be conducted at Screening, Baseline, Week 24, Week 48, Months 18, 24, 30, 36/EOS, and at any Early Termination Visit.

• Distance walked measured by 6MWT

Assessments will be conducted at Baseline, Week 24, Week 48, Months 18, 24, 30, 36/EOS, and at any Early Termination Visit.

• Joint ROM (ankle, knee, hip, and shoulder)

Assessments will be conducted at Baseline, Week 24, Week 48, Months 18, 24, 30, 36/EOS, and at any Early Termination Visit.

• MRI of liver to evaluate liver and spleen volume

Assessments will be conducted at Screening, Week 24, Week 48, Months 18, 24, 30, 36/EOS, and at any Early Termination Visit.

- MRI of brain and cervical spine to evaluate clinical soft tissue and/or bone
  - Assessments will be conducted at Baseline, Week 48, Month 24, Month 36/EOS, and at any Early Termination Visit.
- Neurocognitive abilities by WASI-II, WPPSI-IV, or BSID-III, and by VABS-II Assessments will be conducted at Baseline, Week 24, Week 48, Months 18, 24, 30, 36/EOS, and at any Early Termination Visit.
- Histopathological exam of liver tissue
- Immune response to AAV2/6, ZFNs, and IDS measured in plasma
  Assessments will be conducted at Screening, Baseline, Weeks 2, 4, 6, 8, 12, 16, 24, 36, 48,
  Months 15, 18, 21, 24, 27, 30, 33, 36/EOS, and at any Early Termination Visit.

AAV-related research biomarkers will also be assessed at baseline.

CTI will be analyzing the change from baseline in Plasma IDS Activity, CSF Pressure, Biomarkers, and MRI of Brain and Neck. All other exploratory analyses will be performed by a third party at Sangamo's discretion.

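### Half-detection-limit imputation gives undetected hIDS integration and vector-genome results a positive value, and understates rises from a non-detect baseline

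*Protocol*

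**What the plan says.** The imputation rule appears twice in the SAP. Section 4.5 says: "If laboratory result is below detection limit, it will be imputed to half of detection limit in table and figure". The opening of Section 6, which governs the secondary and exploratory endpoints, says: "If the result is below detection limit, it will be imputed to half of detection limit in table and figure". Section 6 also halves any result that carries a less-than sign. Neither section makes an exception. Both leave listings alone; Section 6 puts it as "The result will be listed as is in listings".

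Two molecular endpoints fall under the rule as written:

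- **Gene modification (exploratory).** SAP 6.3 names "Percentage and durability of gene modification at the albumin locus in liver tissue obtained at biopsy", and adds "Assessments will be conducted at Baseline, Week 24, and Week 48". It states that "Exploratory endpoints will be summarized by presenting descriptive statistics of actual values and changes from baseline at each visit". Protocol Appendix 4 identifies the assay for the transgene: efficiency "in targeting insertion of hIDS donor transgene to the liver will be measured by site specific molecular analysis of integration events" at the albumin locus. Protocol 13.6 defers the analysis details for exploratory endpoints to the SAP.
- **Vector clearance (secondary).** SAP 6.2 plots vector genomes in plasma, saliva, urine, stool and semen over time by cohort. Protocol 6.3 includes a pre-infusion sample.

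Neither document gives an LOD for either assay, or says whether a non-detect is reported as 0, as not detected, or as below a limit.

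**The concern.** LOD/2 is a reasonable convention for an analyte that is always present and sometimes too low to quantify. Pre-infusion hIDS integration is different. No vector has been given, and Protocol 4.2 excludes prior gene therapy, so the true value is zero. A Baseline entry of LOD/2 is then known to be wrong, and it is subtracted from every detected value that follows.

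Integration is the direct evidence that the mechanism works. With about two subjects per cohort, the most informative statement is how many of those biopsied had detectable integration. The SAP plans no such count. Its tables would instead show a positive percentage for non-detects, a reduced rise for detects, and partial persistence where the signal has been lost, although durability is part of the endpoint. In the clearance figures, a sample type that has become negative would be drawn at a positive level.

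**Working it through.** The plan gives no figure of its own on this point, so there is none to reproduce. Write L for the LOD and x for a detected post-infusion value.

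**Inputs**

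- Imputed value L/2: SAP 4.5 and 6.
- True pre-infusion integration 0: inferred from the design and Protocol 4.2.
- Biopsies at Baseline, Week 24 and Week 48; actual values and changes summarised: SAP 6.3.
- Two subjects per cohort: SAP 3.1.
- Reference level 0.01% of alleles: Protocol 8.1.1, "as little as 0.01% of albumin alleles to hIDS synthesis would yield potentially therapeutically beneficial IDS levels".
- L is not stated; assumed range 0.001% to 1% of alleles.

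**1. Detected rise from a non-detect baseline.** True change is x − 0 = x. Under the rule it is x − L/2. The shortfall is L/2, or L/(2x) as a fraction.

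| x | Change under the rule | Understated by |
|---|---|---|
| L | 0.5L | 50% |
| 2L | 1.5L | 25% |
| 5L | 4.5L | 10% |
| 10L | 9.5L | 5% |
| 100L | 99.5L | 0.5% |

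**2. Non-detect at both visits.** The tabulated level is L/2 each time. The change is L/2 − L/2 = 0, so no false rise appears.

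**3. Cohort of two, both non-detect at Baseline; later one non-detect and one at 2L.**

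- Mean level under the rule: (2L + L/2)/2 = 1.25L. With the non-detect counted as 0: 2L/2 = L. The rule is 25% higher.
- Mean change under the rule: (1.5L + 0)/2 = 0.75L. With zeros: L. The rule is 25% lower.
- The post-infusion non-detect could truly lie anywhere from 0 to L, so the true mean level and the true mean change both lie between L and (2L + L)/2 = 1.5L. The imputed mean level, 1.25L, is inside that range. The imputed mean change, 0.75L, is below all of it.

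These ratios do not depend on L.

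**4. Durability.** Week 24 at L, Week 48 undetected. Actual values read L then L/2, that is (L/2)/L = 50% retained. Changes from baseline read L − L/2 = L/2 then 0, a complete loss. The two columns of one table would disagree about the same subject.

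**5. Size against the 0.01% level.**

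| Assumed L | L/2 | Multiple of 0.01% |
|---|---|---|
| 0.001% | 0.0005% | 0.05 |
| 0.01% | 0.005% | 0.5 |
| 0.1% | 0.05% | 5 |
| 1% | 0.5% | 50 |

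The imputed value reaches 0.01% when L = 0.02%.

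**The case against.** The case for leaving the rule alone has several parts.

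- **The raw data stay visible.** By-subject listings show each result unimputed, and with about two subjects per cohort a reader can count the non-detects. This stands. The tables lack the count, but the planned output does not hide it.
- **The trigger is not certain.** If the laboratory reports 0 or not detected, the rule may not apply. Protocol 9.20 speaks of PCR specimens reported as negative or undetectable. This stands, and makes the point conditional. The SAP should settle it.
- **It may not govern this analysis.** SAP Section 4 assigns all exploratory analyses to the contract research organisation. Section 6.3 assigns it a short list that does not name gene modification, unless biomarkers covers it, and leaves the rest to a third party. The conflict is real, but neither passage exempts the endpoint from Section 6, and it does not touch vector clearance, which is secondary.
- **The bias in change is conservative.** For integration with a non-detect baseline it is downward only, and it is small well above the LOD. This stands.
- **A post-infusion non-detect is not known to be zero.** True, so LOD/2 is defensible for that level. It is not defensible for the pre-infusion biopsy.
- **The endpoint is wider than insertion.** Appendix 4 also measures indels, which may have a sequencing background. The zero-baseline argument applies to hIDS integration only.

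A reader might infer that untreated livers would be classed as edited, or that every reported rise is understated. The documents support neither: the plan has no edited category, and the shortfall arises only from a baseline reported as below a limit. Nor is 0.01% an expected level; Protocol 8.1.1 gives it as a minimum that might be beneficial.

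**Conclusion.** The point holds conditionally. As written, the SAP's blanket rule covers hIDS integration and vector-genome PCR. If non-detects are reported as below a limit, it puts a value known to be false into the pre-infusion integration baseline. A detected rise from that baseline is then understated by LOD/2, and tabulated or plotted non-detects are given positive values.

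The relative effects follow from the rule alone, whatever the LOD. The absolute effect cannot be fixed: over the assumed LOD range, the imputed value runs from far below to far above the 0.01% level. It would therefore be wrong to conclude that an undetected biopsy will necessarily be shown at or above a potentially beneficial level.

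The primary safety endpoint does not depend on this, and the study is descriptive. The criterion for ending vector sampling in Protocol 9.20, three consecutive negative specimens, does not use imputed values. The point is worth correcting because the tables and figures would misstate the most direct evidence of mechanism and durability, and the correction is nearly free.

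**What to change.** Amend SAP 4.5 and 6 as follows.

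1. Exempt albumin-locus hIDS integration and vector-genome PCR from LOD/2 imputation.
2. State each assay's LOD and how the laboratory reports a non-detect.
3. Tabulate number detected over number assayed, by cohort and visit (and by sample type for vector genomes).
4. Show non-detects as <LOD in tables, and with a distinct symbol on an LOD line in figures.
5. Summarise by median and range with non-detects ranked lowest, in place of means of imputed values.
6. When computing change in integration, count a non-detect pre-infusion result as 0. Report any detected pre-infusion signal as measured, since it would indicate assay background and should not be overwritten.
7. Keep measured baselines for indels.
8. Reconcile SAP Section 4 with Section 6.3 on who analyses gene modification, so that whoever does it applies the same rule.

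The cost is SAP wording and one extra table column, with no new data. The downside is that no mean is shown when some values are undetected.
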